8.3 Unanticipated Problems Involving Risks to Participants or Others (UPIRPO)

JHM IRB defines UPIRPOs as events or information that is unexpected in terms of nature, severity, or frequency given the research procedures described in the protocol, the informed consent form, and the characteristics of the participant populations AND indicates that participants or others are at greater risk of harm (physical, psychological, economic, or social) than previously known or recognized. Events meeting the JHM IRB requirements for UPIRPOs (https://www.hopkinsmedicine.org/institutional_review_board/guidelines_policies/organization_policies/103_6b.html) are reported promptly to JHM IRB.

8.4 **Reporting Requirements**

SAEs will be reported to the overall PI, and the IRB.

SAE and UPIRSO Reporting to the IRB:

• Events meeting the JHM IRB requirements for UPIRSOs will be reported promptly to the IRB.

The MedWatch report will be submitted to the FDA through the voluntary reporting method by the PI.

A MedWatch 3500A form must be completed and submitted to the FDA as soon as possible, but no later than 10 days of first knowledge or notification of event (5 days for fatal or life-threatening event).

MedWatch 3500A form can be found at:

https://www.fda.gov/safety/medical-product-safety-information/medwatch-forms-fda-safety-reporting

8.5 Supportive Care

8.5.1 All supportive measures consistent with optimal patient care will be given throughout the study.

9 STUDY CALENDAR

MONTHLY Calendar

Test / Procedure	Pre-	Surger	POD	POD	POD	POD	POD	POD	POD	POD
	study	У	1	3	4	5	0	/	14	<30
Informed consent	Х									
Medical history	Х									
Eligibility criteria	Х									
Vital signs ²	Х		Х	Х	Х	Х	Х	Х	Х	
Physical examination ²	X		Х	Х	Х	Х	Х	Х	Х	
CBC with diff ²	Х			X ³						
Urine pregnancy test ⁴	X									
Pain Score ²	Х	Х	Х	Х	Х	Х	Х	Х	Х	Х
Randomization and record of treatment group		Х								
Telephone or In- person Follow up									Х	Х
Pre-operative imaging (US or CT scan)	Х									
Post-operative imaging (US or CT Scan) ⁵								X ³		

1 All Pre-study/Screening procedures should be completed within 24 hours of study enrollment

2 To occur if the patient is still admitted, or seen in follow up

3 To occur at the discretion of the surgeon when clinically warranted

4 Required for any female greater than 10 years old prior to receiving general anesthesia

5 If patient continues to have an elevated WBC, pain on exam, a fever within the last 24 hours or is unable to tolerate a diet.

10 STUDY PROCEDURES

Screening:

Informed Consent

Pre-op Physical exam: Height, weight, abdominal exam

Review of medical history/baseline symptoms including pain score

Pre-op Vitals: heart rate, blood pressure, respiratory rate, pulse oximetry, temperature

Pre-op pain score

Pre-op Labs: CBC w/diff, pregnancy test if warranted

Pre-op imaging: Ultrasound or CT scan

Surgery:

Successful appendectomy will be defined as removal of the appendix and appropriate closure of the cecum.

After successful appendectomy and identification of complex appendicitis, the patient will be randomized into the standard of care arm, or the standard of care with antibiotic instillation arm.

Post-operative monitoring:

Post-operative inpatient Physical exam: abdominal exam

Post-operative inpatient Vitals: heart rate, blood pressure, respiratory rate, pulse oximetry,

- temperature
- Post-operative pain score

Post-operative Inpatient Labs: CBC w/diff if the patient remains hospitalized and is deemed clinically necessary by the surgeon

Post-operative imaging: will occur on POD7 (+/- 1 day) if the patient is still hospitalized and continues to have severe or recurrent abdominal pain, is unable to tolerate a diet, was febrile within the last 24 hours and if clinically warranted has a recent CBC with an elevated WBC.

Follow-up appointment:

Outpatient follow up Physical exam: abdominal exam

Outpatient follow up Vitals: heart rate, blood pressure, respiratory rate, pulse oximetry, temperature Pain score

11 CRITERIA FOR EVALUATION AND ENDPOINT

11.1 Efficacy

Our study is looking to investigate the feasibility of using intra-abdominal antibiotic instillation following a successful appendectomy for acute complex appendicitis. Within this study we will investigate the incidence of deep organ space surgical site infection after a one-time dose of intra-peritoneal antibiotic instillation following a successful appendectomy for acute complex appendicitis. We will review length of stay, inpatient pain medication use, inpatient pain scores, and superficial surgical site infection of the two groups. We will also review complications and any need for further intervention. Each patient will be followed for a total of 30 days post-operatively.

12 STATISTICAL CONSIDERATIONS

A JHACH database manager will create a REDCap database for the study on the passwordprotected JHACH secure network. A Pediatric Surgery Research Fellow will enter data, and the Principal Investigator will check the initial data on six participants for accuracy and completeness and spot-check the data entry independently at least once a month.

All data will be checked for completeness and consistency at the end of the study. Tabular and graphical methods will be used to explore the distribution of the variables. Baseline demographic and clinical characteristics will be summarized using descriptive statistics for continuous (mean, standard deviation, median, range) and categorical variables (counts, percentages). Baseline differences between the groups will be evaluated using independent t-test or

Mann Whitney U test for continuous variables as appropriate, and Chi-squared or Fisher's exact test for categorical variables as appropriate. All statistical analyses will be performed with SAS v 9.4 or a newer version.

Analysis for Aim 1.

The primary aim of this study is to determine the feasibility and safety of the use of antibiotic solution instillation following intraoperative diagnosis of complex appendicitis. We will determine feasibility by the percentage of eligible participants who (1) agree to participate, and (2) complete all intervention sessions and measurement time points. Safety will be determined by adverse events associated with the use of intra-peritoneal antibiotic instillation for the treatment of peritonitis caused by complex appendicitis. For feasibility, we will report the proportions with corresponding 95% confidence intervals for eligibility, recruitment, enrollment, withdrawals and drop outs, and study completion. We will also collect information on barriers and issues of implementation. The study will be deemed feasible if >50% of potential participants agree to participate and at least 75% of them complete all measurement time points. These benchmarks are based on a previous similar study completed in this population. [29]. For safety we will report the incidence of adverse effect with the corresponding 95% confidence interval.

Analyses for secondary aims

We will perform an exploratory efficacy analysis to compare the antibiotic solution instillation group and the control participants on outcome measures. We will initially compare categorical outcomes using Chi-squared or Fisher's exact test as appropriate and independent t-test or Mann Whitney U test for continuous variables as appropriate. We will attempt to use logistic or linear regression as appropriate for the outcome measure to adjust for baseline characteristics that differ between the groups. The main analysis for this aim will be a modified intention-to-treat for the primary analysis. For this analysis, patients will be compared in the two arms based on how they were randomized and it will include all patients that were randomized and received surgery. We will also perform supportive per protocol and as treated analyses. Based on historical data from our institution, we anticipate that <1% of patients who are initially randomized to one arm may switch to the other arm during surgery and approximately <1% may not complete the surgery. These patients will be considered as a protocol violation and will be excluded from the per protocol analysis. The as treated analysis will group the patients according to the type of surgery they actually received and exclude those that did not complete or receive surgery. The analyses for this aim will be exploratory, as the study is not powered to detect clinically important differences between groups using these analyses. However, the findings from these analyses will be used to guide the design of a future larger study that will include appropriate sample size estimations or power analyses.

Attrition and Missing Data:

We will make every effort to reduce attrition. Missing data will be characterized and examined for non-randomness. Missing data will not be imputed.

Sample size justification:

The primary aim of this study is to assess feasibility of the proposed intervention to inform a future larger randomized controlled trial. Therefore, the sample size is not based on a power analysis. A sample size of 36 participants (18 intervention and 18 control) is appropriate to provide feasibility data that will help refine our intervention and measurements for a future larger study.[30] This sample size will allow us to estimate a conservative participation of 70% with a confidence interval of 53-87%. In a similar study conducted by the PI previously, 85% of recruited families consented to randomization and >93% of those families completed all study assessments.

Based on current estimates in our institution, we anticipate 350 appendectomies to be performed each year. Assuming the average documented 20% perforation rate, we anticipate 70 appendectomies for complicated appendicitis each year. Therefore, we will have an eligible pool of 70 patients with intra-operatively diagnosed complicated appendicitis. [29]

Study Monitoring and stopping rules:

All patients will be monitored in the post-operative period, particularly the first 48 hours following surgery. Given the study involves a single dose of intra-peritoneal antibiotic instillation any drug side effects will likely occur within the first 12 hours of treatment. At any time in the study, if a patient suffers an adverse event secondary to intra-peritoneal antibiotic instillation, all study activity will be suspended until a full investigation is completed. The study will only be reinstated after consultation with the Johns Hopkins All Children's Hospital IRB. Patients with severe allergies to cephalosporins or penicillin will be excluded from the study.

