1 OBJECTIVES

1.1.1 Primary objective

To evaluate the feasibility and safety of the use of antibiotic solution instillation following intraoperative diagnosis of complex appendicitis. We will determine feasibility by the percentage of eligible participants who (1) agree to participate, and (2) complete all intervention sessions and measurement time points. Safety will be evaluated by adverse events associated with the use of intra-peritoneal antibiotic instillation for the treatment of peritonitis caused by complex appendicitis.

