Patients will undergo telephone, telemedicine visit, or in-person clinic follow-up within 30days of their discharge following their appendectomy. If patients present with symptoms at these checks or independently present to an emergency department, they will undergo routine evaluation and imaging as clinically indicated. Other parameters that will be tracked include development of superficial or deep surgical site infection, inpatient pain scores, inpatient pain medication use, and post-operative length of stay.

An independent clinical endpoint committee will be formed to evaluate for study related complications and endpoints. For consistency and future ease of a prospective multicenter trial, definitions of intraoperative findings of complicated appendicitis, postoperative percutaneous drainage or aspiration of intraperitoneal fluid collection, surgical site infection, postoperative sepsis, readmission and/or reoperation will be reported according to the National Surgical Quality Improvement Program Pediatric Operations Manual, January 2022 edition. [31]

We will evaluate patient retention and recruitment along with the process of instilling antibiotic solution into the intra-peritoneal space in this feasibility study. We will primarily focus on recruitment, enrollment, and retention rates in this pilot study. We will also evaluate patient outcomes associated with intra-peritoneal instillation of antibiotics to determine not only postoperative complication rates, but also length of stay, pain scores, pain medication use, superficial surgical site infections, and adverse events related to the antibiotic instillation. Patients and their families will be blinded to their randomized treatment groups, and will be followed for 30 days following appendectomy.

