8.1 Adverse Events (AEs)

An adverse event is the appearance or worsening of any undesirable sign, symptom, or medical condition occurring after starting the **study intervention** even if the event is not considered to be related to study intervention. For the purposes of this study, the terms toxicity and adverse event are used interchangeably. Medical conditions/diseases present before starting study drug are only considered adverse events if they worsen after starting study intervention. Abnormal laboratory values or test results constitute adverse events only if they induce clinical signs or symptoms, are considered clinically significant, or require therapy.

AEs will be collected from the date of the operative intervention (with or without instillation of antibiotics) to 30 days after the operative date. Given the one-time study intervention and dosing timeline, any adverse effects should be seen well within the first 48 hours after administration. However, we will continue to review, document, and intervene on any adverse events that occur within the first 30 days following surgery.

Information about adverse events, whether volunteered by the participant, discovered by investigator questioning, or detected through physical examination, laboratory test or other means, will be collected, recorded, and followed as appropriate.

The occurrence of adverse events should be sought by non-directive questioning of the participant at each visit or phone contact during the study. Adverse events also may be detected when they are volunteered by the participant during or between visits or through physical examination, laboratory test, or other assessments. As far as possible, each adverse event should be evaluated to determine at a minimum:

- 1. The severity grade based on CTCAE v.5 (grade 1-5)
- 2. Its relationship to the study intervention (definite, probable, possible, unlikely, unrelated)
- 3. Its duration (start and end dates or if continuing at final exam)
- 4. Whether it constitutes an SAE

All adverse events are expected to be treated appropriately. Once an adverse event is detected, it will be followed until its resolution.

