8.2 Serious Adverse Events (SAEs)

Information about all serious adverse events is collected and recorded. A serious adverse event is one which meets any of the following criteria:

- Is fatal or life-threatening
- Results in persistent or significant disability/incapacity
- Causes congenital anomaly or birth defect
- Requires inpatient hospitalization or prolongation of existing hospitalization, unless hospitalization is for:
 - Routine treatment or monitoring of the studied indication, (such as ongoing pain, fever, constipation, bowel obstruction, surgical site infections, or other infections)
 - Elective or pre-planned treatment for a pre-existing condition that is unrelated to the indication under study and has not worsened since the start of study drug
 - Treatment on an emergency outpatient basis for an event not fulfilling any of the definitions of a SAE given above and not resulting in hospital admission
 - Social reasons and respite care in the absence of any deterioration in the participant's general condition
 - Is medically significant (i.e. defined as an event that jeopardizes the participant or may require medical or surgical intervention to prevent one of the outcomes listed above)

Events that fall within the definitions listed above must be reported as SAEs, irrespective of whether they are judged to be related to treatment or not. If an event is not an AE per the definition in section 9.1, then it cannot be an SAE, even if serious conditions are met (e.g. hospitalization, death due to progression of disease etc.). However, such events may meet JHM IRB reportable definitions as a UPIRSO (see section 9.3). Toxicities unrelated to treatment that

do NOT fall within the definitions above, must simply be documented as AEs in the participant research chart.

Collection of serious adverse events will begin after the patient is randomized into the study intra-operatively and will end 48 hours after administration of the intra-peritoneal antibiotics. It is very unlikely that any serious adverse event will occur given that this study intervention uses a commercially available antibiotic that is routinely administered both parenterally and locally. Adverse events due to intra-peritoneal antibiotic instillation may be difficult to distinguish given that similar antibiotics will be given intravenously.

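### The primary safety result is one rate of instillation-attributed adverse events, with no stated denominator and no all-cause comparison with the randomized control arm

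*Combined protocol and SAP*

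**What the plan says.** **Status of safety.** Section 12, Analysis for Aim 1: "The primary aim of this study is to determine the feasibility and safety of the use of antibiotic solution instillation".

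**Definition.** Three places tie safety to the instillation:
- Section 12: "Safety will be determined by adverse events associated with the use of intra-peritoneal antibiotic instillation".
- Section 1.1.1: "Safety will be evaluated by adverse events associated with the use of intra-peritoneal antibiotic instillation".
- Section 4 lists, among the outcomes to be evaluated, "adverse events related to the antibiotic instillation".

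**Planned statistic.** Section 12: "For safety we will report the incidence of adverse effect with the corresponding 95% confidence interval". It names no arm, denominator, unit of counting (patients or events) or interval method. Section 12 defines analysis populations only under the secondary aims.

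**Attribution.** Section 8.2: "Adverse events due to intra-peritoneal antibiotic instillation may be difficult to distinguish given that similar antibiotics will be given intravenously". Section 4 gives both arms at least 48 further hours of intravenous ceftriaxone and metronidazole. Section 8.1 grades relationship to the intervention on five levels, from definite to unrelated, but no section says which levels count towards the safety result.

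**Collection.** Section 8.1: "AEs will be collected from the date of the operative intervention (with or without instillation of antibiotics"), continuing to 30 days after the operation. It covers events whether or not they are thought related, with a CTCAE grade and a seriousness flag.

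**Between-arm comparisons.** Section 12 plans these for the secondary aims, as an exploratory efficacy analysis. The outcomes in Section 1.1.2 include readmission, post-operative imaging and abscess needing aspiration or drainage. Section 11.1 adds superficial surgical site infection in the two groups. All-cause adverse events are not named in either list.

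**The concern.** On the causal reading, only Arm B can contribute events to the primary safety result, and each event enters only if someone judges that the instilled ceftriaxone caused it. That judgement is hard here: the patient is also receiving the same drug intravenously and recovering from surgery for complex appendicitis. A low reported rate could mean that the instillation is harmless, or that events were ascribed to the intravenous drug or to the disease. A high rate could equally reflect generous attribution.

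A concurrent randomized control removes the need for that judgement, because any excess in Arm B can be estimated from all-cause counts. The plan collects those counts in both arms but specifies no such comparison. At stake is the safety half of the primary aim, which is meant to inform a larger multicenter trial. The suspension rule in Section 12 rests on the same kind of judgement, since it applies "if a patient suffers an adverse event secondary to intra-peritoneal antibiotic instillation".

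**Working it through.** The documents give no numerical figure for safety, so there is none to reproduce. The only precision figure in Section 12 concerns participation.

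**Inputs.** 18 intervention and 18 control patients (Section 12, sample size justification). Adverse-event rates are not given, so every rate below is an assumption. All 36 are taken as treated as randomized; Section 12 expects less than 1% to switch arm and about less than 1% not to complete surgery.

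**1. Dependence on attribution.** Let q be the background rate of patients with an event, equal in both arms (no instillation effect), and m the share attributed to the instillation. The apparent attributed rate is q × m.

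| q (assumed) | m = 0 | m = 25% | m = 50% | m = 100% |
|---|---|---|---|---|
| 10% | 0% | 2.5% | 5% | 10% |
| 20% | 0% | 5% | 10% | 20% |
| 50% | 0% | 12.5% | 25% | 50% |

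The true effect is zero in every cell. The planned statistic ranges from 0 to q according to m alone. The risk difference between arms has expectation q − q = 0 in every row, whatever m is.

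**2. Effect of the unstated denominator.** With zero events, the two-sided exact (Clopper-Pearson) upper limit is 1 − 0.025^(1/n).
- n = 18 (Arm B): 1 − 0.025^(1/18) = 18.5%.
- n = 36 (everyone): 1 − 0.025^(1/36) = 9.7%.

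The same observation gives limits that differ about twofold. If attributed events can occur only in Arm B, 36 is not a meaningful denominator, but the text does not exclude it.

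**3. What the by-arm comparison would give.** Newcombe 95% interval for the risk difference, 18 v 18:
- 6 v 3 patients: 6/18 − 3/18 = +16.7 points. The Wilson limits are 16.3% to 56.3% for 6/18 and 5.8% to 39.2% for 3/18.
  - Lower limit: 16.7 − √[(33.3 − 16.3)² + (39.2 − 16.7)²] = −11.6.
  - Upper limit: 16.7 + √[(56.3 − 33.3)² + (16.7 − 5.8)²] = +42.0, using unrounded values.
- Equal counts of 2, 5 or 9 per arm: 0 ± 23, ± 28 or ± 30 points.

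Exact Fisher power at assumed rates is 20% for 10% v 30%, and 36% for 20% v 50%. The comparison can describe; it cannot test.

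**4. Serious events.** Section 8.1 flags seriousness for adverse events collected to day 30. Section 8.2 ends serious-event collection 48 hours after the intra-peritoneal dose. Control patients receive no such dose, so their window has no defined end. Serious events to day 30 in both arms therefore cannot be assumed to be available.

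**The case against.** **Associated may be meant loosely.** It could cover any event after instillation, and the sentence giving the statistic has no explicit causality filter. The wording in Section 4 favours the causal reading. On the loose reading, the result is still a single rate in post-operative patients that cannot be interpreted without the control rate. Both readings lead to the same fix.

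**The trial is too small to compare adverse events.** The intervals are indeed wide, and this part of the objection stands: the comparison must be labelled descriptive. Section 12 already accepts unpowered comparisons for efficacy outcomes, so size is no reason to omit one for safety.

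Some stronger readings are tempting, but the documents do not support them:
- *That causality is judged by staff who know the arm.* Section 8.1 does not say who grades it. Section 4 describes a PROBE design, blinds caregivers outside the operating room and sets up an independent endpoint committee. Unblinded attribution is a possibility left open, not a stated fact.
- *That attribution is impossible or admitted to be unreliable.* Section 8.2 says only that it may be difficult.
- *That the control arm goes unused for harms.* Abscess, readmission and surgical site infection are compared or reviewed by arm. The gap is all-cause adverse events.
- *That the 18.5% limit measures the defect.* It follows from having 18 treated patients and would apply under any attribution rule. The plan sets no threshold for declaring the instillation safe, so the limit contradicts no stated conclusion.

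**Conclusion.** The point holds in this form. The primary safety result is defined by events linked to the instillation. It is to be reported as one incidence with no denominator or control comparison, in a setting where the protocol itself expects attribution to be difficult. All-cause events by randomized arm would be less open to bias, and Section 8.1 already collects them in both arms to day 30.

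The possible distortion equals the background event rate multiplied by the share attributed: 0 to 20 percentage points at an assumed 20% background rate. The documents give no rate from which to narrow this. The gain from the fix is a safety estimate that does not depend on causality judgement; it does not bring precision. This should be changed before analysis, but it does not undermine the conduct of the trial. The conclusion rests on the causal reading of the endpoint for the attribution problem; the missing comparison stands on either reading.

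**What to change.** In Section 12, Analysis for Aim 1:
1. Make the primary safety summary the number and percentage of patients with at least one adverse event of any cause, and with at least one of grade 3 or higher, to day 30 by randomized arm. Give risk differences with 95% confidence intervals, name the interval method, and label the comparison descriptive.
2. Keep attributed events in Arm B as a secondary summary. State the denominator (the 18 treated, if all are treated as planned), which causality grades count, who assigns them and whether that person is blinded. Note that 0/18 leaves a two-sided exact upper limit of 18.5%.
3. Add serious adverse events by arm once Sections 8.1 and 8.2 are reconciled on the collection period and on how it is defined for control patients.

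The cost is analysis wording for items 1 and 2, because the data are already to be collected. Item 3 needs a protocol reconciliation. No extra patients are required; the price is wide, descriptive intervals.

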Study participants will be randomized in a 1:1 ratio using permuted blocks of 4 and 6 using a computer-generated randomization scheme. The treatment category assignments will be placed in consecutive numbered envelopes concealed from study staff until randomization. In the operating room, once the patient is diagnosed with complicated appendicitis, then the next sequential envelope will be opened and the patient will be assigned to that treatment arm. The surgeon and team administering the treatment will not be blinded; however, patients, their families, and hospital caregivers outside of the operating room will be blinded to the treatment. Post-operative protocols will be the same for both groups and includes continuation of intravenous antibiotics (Study Schema, and Fig 1). Once complex appendicitis is diagnosed, and a successful appendectomy occurs, then the patient will be transitioned to intravenous ceftriaxone (50mg/kg/day, maximum 2g daily) and metronidazole (30mg/kg/day) post-operatively. Both study groups will receive a minimum additional 48 hours of intravenous ceftriaxone and metronidazole, as per our weight based current standard of care. Patient status and post-operative recovery back to baseline will dictate discharge or continued hospitalization. Pending their clinical course, patients will be either transitioned to broadspectrum oral antibiotics or continued on intravenous ceftriaxone and metronidazole until their discharge from the hospital. Our standardized discharge criteria includes: temperature less than 38.5°C for the previous 24 hours, improved abdominal pain without the use of narcotics, and tolerance of enteral intake. Once these criteria have been met, and at the surgeon's discretion, the patient will be discharged home with routine follow-up (either a clinic visit, telemedicine visit, or a phone call) within 30 days after surgery.

If the patient remains hospitalized on post-operative day 7 (plus or minus 1 day) related to postoperative care of complicated appendicitis, and does not meet discharge criteria as listed, then they will undergo subsequent imaging studies (abdominal ultrasound or CT abdomen-pelvis) to evaluate for intra-abdominal abscess or phlegmon. If patients are found to have an abscess or phlegmon, they will continue to receive ongoing antibiotic treatment with or without percutaneous aspiration and/or drainage at the discretion of the surgeon and interventional radiologist.

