5.1 Inclusion Criteria

- 5.1.1 Patient diagnosed with acute appendicitis and are scheduled to undergo urgent appendectomy
- 5.1.2 Patient is between 3-18 years of age at time of appendectomy
- 5.1.3 Patient has intraoperative findings of complex appendicitis defined by: visible hole in the appendix, extra-luminal fecalith, diffuse fibropurulent exudate outside the RLQ/pelvis, or intraperitoneal abscess
- 5.1.4 Patient weighs equal to or greater than 20kg at time of surgery

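### Minor: the exploratory adjusted comparisons pick covariates by between-arm difference, which under randomization is chance; naming a prognostic covariate in advance is better for continuous outcomes and nearly free

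*Combined protocol and SAP*

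**What the plan says.** Section 12 describes two steps that touch on baseline balance.

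- In the general paragraph: "Baseline differences between the groups will be evaluated using independent t-test" or a Mann-Whitney test for continuous variables, and "Chi-squared or Fisher's exact test for categorical variables as appropriate".
- Under the analyses for secondary aims, after unadjusted comparisons of the outcomes, the team will attempt "logistic or linear regression as appropriate for the outcome measure to adjust for baseline characteristics that differ between the groups".

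The section names no covariate, no threshold for a difference and no maximum number of covariates. It does not say that the baseline tests do the selecting, although that is a natural reading.

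Section 4 gives 1:1 allocation in permuted blocks, with assignments "concealed from study staff until randomization". The main secondary analysis compares patients as randomized, among those who had surgery. Section 12 calls these analyses exploratory and unpowered, but adds that "the findings from these analyses will be used to guide the design of a future larger study".

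**The concern.** With concealed randomization, arms compared as randomized differ at baseline only by chance. Observed imbalance therefore says nothing about whether a variable predicts length of stay or pain. A strongly prognostic variable that happens to be balanced is left out, and its gain in precision is lost. A variable unrelated to the outcome that happens to be imbalanced is put in, and costs precision.

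The model also cannot be written down before the data are seen, and two analysts could fit different models to the same data. With 36 patients, precision on the continuous outcomes is scarce, and these are estimates the plan intends to carry into the design of the larger trial.

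**Working it through.** The documents give no variance, correlation or significance level for the adjusted analysis, so there is no figure of the plan's to reproduce.

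**Inputs**
- 18 per arm, 36 in total (Section 12, sample size justification).
- Meaning of a difference: not stated. Two readings are assumed: two-sided p<0.05, and an absolute standardized mean difference (SMD) above 0.3.
- Correlation rho between covariate and outcome: not stated. Assumed 0.3, 0.5 and 0.7.
- One candidate covariate, linear model, normal data.

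**Step 1: how often the covariate enters.** Under p<0.05, 5% of the time by construction. Under |SMD|>0.3, the t statistic is 0.3/sqrt(2/18) = 0.9 on 34 degrees of freedom, so the probability is 2 x P(t34 > 0.9) = 37.4%. Neither depends on rho: prognostic value plays no part in entry.

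**Step 2: what naming the covariate in advance gives.** Averaged over randomizations, variance relative to no adjustment is (1 - rho²) x (n - 3)/(n - 4). At n = 36 the factor is 33/32 = 1.031.
- rho 0: 1.031
- rho 0.3: 0.91 x 1.031 = 0.94
- rho 0.5: 0.75 x 1.031 = 0.77
- rho 0.7: 0.51 x 1.031 = 0.53

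Break-even is where (1 - rho²) x 33/32 = 1, so rho = sqrt(1/33) = 0.174.

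**Step 3: what the planned rule gives.** Simulation, 200,000 trials per correlation; a repeat agreed within simulation error.

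| rho | Variance, p<0.05 rule / pre-named | Variance, SMD>0.3 rule / pre-named | Type I error, p rule | Type I error, SMD rule |
|---|---|---|---|---|
| 0.3 | 1.048 | 1.010 | 4.8% | 4.6% |
| 0.5 | 1.211 | 1.043 | 4.4% | 3.8% |
| 0.7 | 1.663 | 1.136 | 3.6% | 2.7% |

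The excess is about 5%, 21% and 66% under p<0.05, and about 1%, 4% and 14% under the SMD reading. At rho 0.2 it is about 1% and 0%. Type I error is at or below 5% throughout.

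**Step 4: the price of naming a useless covariate.** At n = 36 it is 33/32, or 3.1% more variance on average. Missing data are not imputed; if only 75% of patients could be analysed (36 x 0.75 = 27), it is 24/23, or 4.3%. These are averages over randomizations. In a single trial the inflation factor exceeds 1.12 in 5% of randomizations and 1.22 in 1%.

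**The case against.** The strongest reply is that little hangs on this. The adjusted step is only to be attempted, it follows unadjusted comparisons, and the plan itself calls it exploratory and unpowered. The primary aim is feasibility and safety. All of that stands, and it is why the point is minor.

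A second reply is that the losses depend on assumed correlations and on how a difference is defined. That also stands. Near rho 0.2, or under the SMD reading with a weak covariate, the loss is negligible.

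Three stronger readings are tempting, and the documents do not support them.

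- *That the rule produces false positives.* In the single-covariate check it does not; it is conservative.
- *That the loss grows because there are many candidates.* Sections 5.1 and 10 list about ten possible baseline variables. If ten were independent, one were prognostic and that one were named, the excess under p<0.05 would be about 14% at rho 0.3 and 33% at rho 0.5. But the documents do not say which variable is prognostic. With the named covariate picked at random, these figures fall to about 5% and 2%. If five candidates each correlate 0.3 with the outcome, the SMD rule has about 22% less variance than one named covariate. The sign depends on facts the documents do not give.
- *That a covariate named in advance can never cost more than 3%.* The 3% is an average, not a bound for one trial, and it does not apply to logistic models.

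In the per-protocol and as-treated analyses, baseline differences need not be pure chance. The plan expects under 1% to switch arms and under 1% not to complete surgery, so this hardly matters.

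**Conclusion.** The point holds as a minor one, limited to the exploratory adjusted comparisons. The plan states a poor selection rule rather than merely leaving out detail. For continuous outcomes with one candidate covariate, the loss against naming it in advance runs from about 1% to 66% in variance over correlations of 0.3 to 0.7, depending on what counts as a difference. It rests on assumed correlations, a linear model and full data on 36 patients. No multi-candidate figure is claimed, and no precision gain is claimed for logistic models of binary outcomes such as abscess or readmission. Nothing here affects the feasibility and safety conclusions.

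**What to change.** In Section 12, report baseline data descriptively and do not use baseline differences to choose covariates. Replace the adjustment phrase with wording such as: *Adjusted analyses of continuous exploratory outcomes will use a covariate named before outcomes are examined, chosen for expected prognostic value and used whatever the observed balance.*

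Examples:
- Pain score on postoperative day 1, adjusted for the preoperative score ("Pre-op pain score" is in the Section 10 screening list, and both time points are on the Section 9 calendar). Section 11.1 speaks only of inpatient pain scores, so the day would have to be named too.
- Length of stay, adjusted for one named severity variable measured before randomization, such as preoperative white cell count from the scheduled blood count, or left unadjusted.
- Operative time, antibiotic use and pain medication use: the same choice, made outcome by outcome.
- Binary outcomes with few events: keep the unadjusted risk difference with a 95% confidence interval as the main summary.

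The cost is a wording change and one decision per continuous outcome. The covariates in these examples are already scheduled. The downside is the average 3% in variance (4.3% with 27 patients) if a named covariate turns out to be unrelated to the outcome.
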